3.2.3. Pharmacodynamic Endpoints

Pharmacodynamic data and parameters will be generated from PRU, LTA and PRI assays:

VerifyNow®P2Y₁₂:

- PRU at each assessment point
- Percent of reversal (%baseline) in ticagrelor antiplatelet activity by PRU at each assessment point
- Maximum PRU
- Maximal percent of baseline PRU
- Time to maximum PRU
- Maximum PRU within 4 hours
- Time to ≥ 180 PRU
- Time to ≥ 200 PRU
- Time to ≥ 220 PRU
- Time to 60%, 80%, and 90% of reversal in PRU

LTA:

- The maximum and final extent of aggregation for up to 4 platelet agonists (20 μ M adenosine diphosphate [ADP], 5 μ M ADP, 1.6 mM arachidonic acid [AA], and 15 μ M thrombin receptor activating peptide [TRAP]), will be recorded at each assessment point.
- Percent of reversal (%baseline) in ticagrelor antiplatelet aggregation
- Maximum platelet aggregation
- Maximum percent of baseline platelet aggregation
- Time to maximum platelet aggregation
- Maximum platelet aggregation within 4 hours
- Time to 60%, 80%, and 90% of reversal in platelet aggregation

VASP by ELISA:

- PRI at each assessment point
- Percent of reversal (%baseline) in PRI at each assessment point
- Maximum PRI
- Maximum percent of baseline PRI
- Time to maximum PRI
- Maximum PRI within 4 hours
- Time to 60%, 80%, and 90% of reversal in PRI
- Time to minimum PRI

3.3. Treatments

Study Drug will refer to PB2452 or matching placebo.

PART A:

PB2452: PB2452 IV infusion, prepared according to the Pharmacy Manual, was administered on Day 1 for up to 48 hours. The total dose for each subject was 18g. The infusion rate was not to

exceed 18g over 30 minutes and the concentration was not to exceed 24g in 250mL. Subjects were not to receive more than 250 mL of study drug infusion within any 1-hour period. Two cohorts were enrolled in Part A, both at a total dose of 18g.

For each cohort, the dose, infusion rate, and duration was communicated from the Sponsor to the study site, PPD, in a Dosing Memo issued prior to initiation of each treatment cohort.

Matching Placebo: 0.9% sodium chloride single IV infusion, administered on Day 1, was delivered at a rate and volume matching the active infusion.

Ticagrelor: Ticagrelor 90 mg oral tablet (immediate release) administered as 180 mg (2 × 90 mg tablets) loading dose plus 90 mg every 12 hours for 4 additional doses.

ASA: During Screening, starting on Study Day -7, subjects received ASA (enteric coated) 81 mg QD to be taken through to the morning of Day 1, prior to receiving study medication. Subjects who were already taking ASA daily before entering the study must have been willing to document self-administered daily 81 mg dose of ASA between Day -7 and -3, accept ASA 81 mg administered at the clinical site between Day -2 and Day 1, and suspend further ASA doses until discharge from the clinical facility.

PART B:

PB2452: PB2452 IV infusion, prepared according to the Pharmacy Manual, was administered on Day 1 for up to 48 hours. For each cohort, the dose, infusion rate, and duration was communicated from the Sponsor to the study site, PPD, in a Dosing Memo issued prior to initiation of each treatment cohort. One cohort in Part B was enrolled, at a total dose of 36 g.

Matching Placebo: 0.9% sodium chloride single IV infusion, was delivered at a rate and volume matching the active infusion.

Ticagrelor: Ticagrelor 90 mg oral tablets (immediate release) was administered as a 180 mg (2 × 90 mg tablets) oral dose every 12 hours for 5 total doses.

4. General Statistical Considerations

All statistical analyses will be conducted using statistical analysis system SAS® Version 9.4 or higher (SAS Institute, Cary, NC). For tables and data listings with no data, titles and footnotes will be presented, and “No data to display” will be presented.

Descriptive statistics for continuous variables will include number of subjects, mean, standard deviation (SD), median, minimum, and maximum, unless otherwise noted. Minimum and maximum will be presented to the same number of decimal places as the raw data, mean and median will be presented to one more decimal place than the raw data, and SD will be presented to two more decimal places than the raw data, unless otherwise specified.

Frequency and percentage will be calculated for categorical variables. Percentages will be presented with 1 decimal place, and if the value is less than 0.1, then “<0.1” will be displayed.

All data will be provided in by-subject listings.

For summary of safety assessments, if there are repeated measurements at a time point, the original measurement at that time point will be used in the summary tables. If the original measurement is missing, the next available measurement at that time point will be used in the summary tables.

Baseline will be defined as the last nonmissing assessment before study drug (PB2452 or matching placebo) administration.

Unscheduled results will not be included in the summary tables except for determining Baseline but will be presented in data listings.

Unless otherwise stated, the following treatment groups will be used in the summaries, where C denotes Cohort:

- 18 g PB2452 (C1)
- 18 g PB2452 (C2)
- 36 mg PB2452 (C3)
- Placebo
- All PB2452 (for safety analyses only)
- All Subjects (for safety analyses only)

Outputs will be provided for Part A and Part B, separately.

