### Pharmacodynamic Endpoints:

#### *VerifyNow®P2Y12:*

- Minimum %inhibition of PRU within 4 hours after the initiation of study drug. %inhibition of PRU is calculated as  $100 * [(PRU_{bsl} - PRU_{trt})/PRU_{bsl}]$ . PRUbsl refers to the PRU value measured before treatment with ticagrelor and PRUtrt refers to the PRU value measured posttreatment with the study drug.
- PRU area under the curve (AUC) for the first 4 hours.
- Proportion of patients with normalized platelet reactivity units within 4 hours after the initiation of study drug. Normalized platelet reactivity is defined as PRU  $\geq 180$ .
- Proportion of patients with  $\geq 60\%$ ,  $\geq 80\%$ , and 100% of PRU response rate within 4 hours after the initiation of study drug. A PRU response rate is defined as the  $100 * (PRU_{trt}/PRU_{bsl})$ .

- Time to 60%, 80%, 100% of PRU response rate within 4 hours after the initiation of study drug
- Duration of 80% and 100% of PRU response rate by PRU.

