The PK profile of PB2452 demonstrated that mean plasma concentrations of PB2452 rapidly declined following the end of infusion across all cohorts. In cohorts 1-3 when PB2452 was administered as a 30-minute intravenous infusion in the absence of ticagrelor, elimination appeared to be biphasic with half-life values ranging from 1.5 to 9.2 hours for the dose range 0.1 g to 1 g. In the presence and absence of ticagrelor, geometric mean observed maximum plasma concentration ( $C_{max}$ ) values and geometric mean area under the plasma concentration versus time curve (AUC) from time zero extrapolated to infinity ( $AUC_{0-\infty}$ ) values of total PB2452 appeared to increase in a dose-proportional manner. The inter-individual variability (geometric mean coefficient of variation [CV%]) for  $C_{max}$  and  $AUC_{0-\infty}$  was low, ranging from 4.8% to 28.9% across Cohorts 1-3. PB2452 appeared to increase mean total plasma concentrations of ticagrelor and TAM compared to placebo, and this effect was dependent on the dose of PB2452. Additionally, PB2452 increased the renal CL of ticagrelor and TAM in a dose-dependent manner.

The PD profile of PB2452 demonstrated that for subjects receiving steady-state ticagrelor, IV infusion of PB2452 (3 to 18 g) restored platelet activity to approximately 100% of baseline using multiple assays of platelet function. The onset of reversal was rapid, occurring at the first assessment of platelet function following initiation of PB2452 infusion (30 minutes in cohorts 4-6 and 5 minutes in cohorts 7-10). The duration of ticagrelor reversal appeared to be dependent on the total dose and infusion duration of PB2452.

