**LTA:**

- Minimum %inhibition of LTA within 4 hours after the initiation of study drug.
- LTA AUC for the first 4 hours.
- Proportion of patients with  $\geq 60\%$ ,  $\geq 80\%$ , and  $100\%$  of LTA response rate within 4 hours after the initiation of study drug. LTA response rate is defined as the  $100 * (LTA_{trt}/LTA_{bsl})$ .
- Time to  $60\%$ ,  $80\%$ ,  $100\%$  LTA response rate within 4 hours after the initiation of study drug.
- Duration of  $80\%$  and  $100\%$  of LTA response rate.

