#### **Pretreatment - Baseline (Day -2)**

- Subjects receive ASA 81mg QD

- Administration of ticagrelor begins in the morning, single dose oral ticagrelor 180 mg (2 x 90 mg), followed by oral ticagrelor 90 mg every 12 hours for 4 additional doses through to Day 1 (2 hours before study drug is initiated; for a total of 5 doses of ticagrelor)
- Urine sampling, PK
- Blood sampling for PD (LTA/PRU/VASP)
- AEs collected

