PB2452 is a specific and selective recombinant human neutralizing antibody IgG1 λ monoclonal fragment antigen-binding antibody that binds with high affinity to ticagrelor and to AR-C124910XX (TAM), the major active circulating ticagrelor metabolite. PB2452 is intended to reverse the antiplatelet effects of ticagrelor in patients who experience major bleeding or who require urgent surgery or intervention. Platelet transfusion has appeared to be inferior to standard care for those taking antiplatelet therapy. ([Baharoglu, 2016](#))

This is a two-part Phase 2A, randomized, double-blind, placebo-controlled, single dose, sequential group study to evaluate the safety, tolerability, PK, and PD of PB2452 vs matching placebo. Part A investigates various dose regimens of PB2452 administered intravenously to older (ages 50 to 64 years) and elderly (ages 65 to 80 years) male and female subjects pretreated with ticagrelor + aspirin (ASA) as part of dual antiplatelet therapy. Part B investigates various dose levels and regimens of PB2452 administered to healthy male and female subjects (ages 18-50) pretreated with a high dose of ticagrelor alone (180 mg) twice daily (BID).

This statistical analysis plan (SAP) is written according to protocol PB2452-PT-CL-0002, version Final 2.0 (Part A) and Final 1.0 (Part B), both dated 29 July, 2019. This SAP will cover the final analysis for both parts, Part A and B, of the study.

2. Objectives

2.1 Primary Objectives:

- To evaluate the safety and tolerability of intravenous (IV) doses of PB2452 vs matching placebo with oral ticagrelor plus ASA pretreatment in older (age 50 to 64 years) and elderly (age 65 to 80 years) male and female subjects in Part A, and, to evaluate the safety and tolerability of intravenous (IV) doses of PB2452 vs matching placebo with a High Dose of oral ticagrelor plus ASA pretreatment in healthy patients (age 18 to 50) in Part B
- To assess the efficacy/PD of IV doses of PB2452 vs matching placebo in reversing ticagrelor antiplatelet activity by measuring P2Y₁₂ reaction units (PRU) with VerifyNow® P2Y₁₂ assay in older (age 50 to 64 years) and elderly (age 65 to 80 years) subjects, and in healthy patients (age 18 to 50) with a High Dose of oral ticagrelor plus ASA pretreatment in Part B

2.2 Secondary Objectives:

- To determine the PK of PB2452 in the presence of ticagrelor, for each of Part A and B
- To determine the PK of ticagrelor and TAM in the presence of PB2452, for each of Part A and B

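### The SAP's only Baseline rule makes the on-ticagrelor Hour 0 sample the denominator of %baseline for PRU, LTA and PRI, whereas the protocol sets PRU baseline before ticagrelor

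*SAP*

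**What the plan says.** SAP Section 4 (General Statistical Considerations) holds the only Baseline definition in the SAP: "Baseline will be defined as the last nonmissing assessment before study drug (PB2452 or matching placebo) administration". It names no type of data. SAP Section 3.3 confirms that study drug means PB2452 or placebo, so ticagrelor is not study drug.

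SAP Section 3.2.3 lists among the PD endpoints "Percent of reversal (%baseline) in ticagrelor antiplatelet activity by PRU at each assessment point", with matching entries for LTA and PRI. Section 11.1 expresses all three assays as actual values and as %baseline. Section 11.2 builds on %baseline the maximal percent of baseline, the times to 60%, 80% and 90%, and the counts of subjects reaching those levels within 30 minutes or 4 hours. None of these sections states the denominator. Section 4.4 refers the reader to Section 11 for PD data handling, but Section 11 covers missing values and gives no baseline.

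The protocol defines the quantity for PRU. In the synopsis and Section 2.2.2 of both Part A and Part B, the PRU baseline term "refers to the PRU value measured before treatment with ticagrelor", and the response rate is 100 times the post-treatment PRU divided by that baseline. For LTA and PRI the protocol uses baseline terms in the same formula without tying them to a sample.

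The SAP presents itself as following the protocol ("This statistical analysis plan (SAP) is written according to protocol PB2452-PT-CL-0002"), and its Section 13 declares no change from it.

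**The concern.** A ratio meant to show reversal of ticagrelor needs the uninhibited platelet function as its denominator. If the denominator is taken while the subject is on ticagrelor, every subject with a nonzero Hour 0 value stands at 100% before any PB2452 is given, and the 60/80/90% thresholds no longer separate reversed from unreversed platelets. Placebo subjects could be counted as having reversed simply by staying as inhibited as they were at Hour 0.

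Reversal measured by PRU is a primary objective in both parts, so this affects how half the PD parameter rows in Section 11.2 would be read. The rule also has an inconsistent fallback. If Hour 0 is missing, the preceding nonmissing PD value is the pre-ticagrelor Day -2 sample, so one table could mix on-ticagrelor and off-ticagrelor denominators.

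**Working it through.** **Which sample the rule selects.** SAP Section 11.1 gives the PD draws before study drug, identical for all three cohorts: Day -3; Day -2, up to 60 minutes before the first ticagrelor dose; and Hour 0, up to 10 minutes before the infusion. SAP Section 10.1.1 places the fifth ticagrelor dose 2 hours before the infusion. Applying Section 4 literally selects Hour 0, on ticagrelor. Applying the protocol's PRU definition selects Day -3 or Day -2.

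**Outputs that depend on the denominator (SAP Section 11.2).**

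| Assay | Parameter rows | Rows using %baseline |
|---|---|---|
| PRU | 10 | 4 (maximal %, times to 60/80/90%) |
| LTA | 7 | 4 |
| PRI | 7 | 4 |
| Total | 24 | 12 |

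LTA may be split into maximal and final aggregation at 5 and 20 µM ADP, which is 4 series. Because the SAP says this is done as appropriate, the expanded counts are upper limits:

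- Parameter series: 10 + 28 + 7 = 45, of which 4 + 16 + 4 = 24 depend on %baseline.
- Responder counts: 3 assays × 3 thresholds × 2 windows = 18, or 6 series × 3 × 2 = 36.
- By-timepoint %baseline summaries: 6 series × 12 post-infusion times = 72 per treatment group.

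**Results that need no assumed values.** Let H be the Hour 0 value and P the pre-ticagrelor value.

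- Under the literal rule %baseline = 100 × post/H. A subject meets 60/80/90% unless the value falls by more than 40/20/10% from H.
- An unchanged placebo subject reads 100 × H/H = 100% and meets all three thresholds at 5 minutes. With P as denominator the same subject reads 100 × H/P. The two rules therefore disagree whenever H is below 60/80/90% of P.
- The protocol also states "Normalized platelet reactivity is defined as PRU" of at least 180. The literal 90% threshold is 0.9 × H, which is below 180 whenever H is below 180/0.9 = 200.

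**Illustration for PRU (assumed values; the documents give no on-ticagrelor PRU).** P = 240, H = 48, which is 48/240 = 20%.

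| | Literal rule (÷ 48) | Pre-ticagrelor rule (÷ 240) |
|---|---|---|
| Placebo unchanged at 48 | 100%, meets 60/80/90% | 20%, meets none |
| PRU needed for 60/80/90% | 29 / 38 / 43 | 144 / 192 / 216 |
| PB2452 subject restored to 240 | 500% | 100% |

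For H from 24 to 96 (10% to 40% of 240), the unchanged placebo subject reads 100% under the literal rule against 10% to 40%. The PRU needed under the literal rule is 14–58, 19–77 and 22–86 for the three thresholds, and full restoration reads from 1000% down to 250%.

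A wider grid (P 200–300, H 10–80) shows the same pattern. The unchanged placebo subject reads 100% against 3% to 40%. The 80% threshold is PRU 8–64 against 160–240. A subject restored to only half of P reads 125% to 1500% under the literal rule and 50% under the other.

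If placebo values keep falling after Hour 0, fewer placebo subjects meet the literal thresholds; a fall to 0.7 × H still meets 60% but not 80% or 90%.

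**Fallback, same illustration.** With Hour 0 missing, a 5-minute PRU of 48 is divided by the Day -2 value of 240 and reads 20%, while a subject with Hour 0 present and the same PRU reads 100%.

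**The case against.** The strongest reply is that the intent is plain. The SAP calls the quantity a percent of reversal, and a ratio that is 100% before treatment cannot be one. The protocol reports that in Phase 1 PB2452 "restored platelet activity to approximately 100% of baseline using multiple assays of platelet function". In Section 3.5 of both protocols, every PD draw at a visit labelled baseline falls before ticagrelor: Day -3, or "Pretreatment - Baseline (Day -2") with SAP Section 11.1 placing that draw before the first dose. Day -1 carries the label but has no PD draw, and Day 1 does not carry it. The Baseline sentence also follows a paragraph about safety summaries, and the explicit change-from-baseline tables are all safety tables. A programming error of this kind would be visible, because Hour 0 would read exactly 100% for everyone with a value. Finally, the SAP plans no between-arm test of %baseline, and the sample size is not based on power.

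Much of this stands. It makes a pre-ticagrelor intent likely, and it means the text does not prove what the programs do. The direct contradiction is with PRU only; for LTA and PRI the protocol leaves the baseline unspecified. The percentages above 100 rest on assumed PRU values, and nothing shows how often Hour 0 would be missing.

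It does not remove the defect. Likely intent does not override an explicit contrary rule in the document that programmers work from. The protocol's definition is also not carried over by reference: the SAP uses 60/80/90% of baseline where the protocol uses 60/80/100% response rates, and it never cites the protocol's baseline term. Intent also leaves open which of the two pre-ticagrelor draws applies.

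**Conclusion.** The concern holds and should be resolved before the PD outputs are relied on. As written, the SAP's only Baseline rule makes the Hour 0 on-ticagrelor sample the denominator for all three assays. For PRU this contradicts the protocol and the SAP's own statement of no change. For LTA and PRI the SAP rule is the only explicit one, and it gives a ratio that does not measure reversal.

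Half of the parameter rows in Section 11.2 (12 of 24), all the 60/80/90% responder counts and the by-timepoint %baseline summaries are affected. Actual values, actual maxima (overall and within 4 hours), time to maximum and times to 180/200/220 PRU are not. The finding that an unchanged placebo subject meets every threshold needs no assumed data; only the illustrative PRU figures do. The affected summaries are descriptive, so the harm is to interpretation, not to a formal test.

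**What to change.** Add to SAP Section 11, in substance: for PRU, for maximal and final aggregation at each ADP concentration, and for PRI, PD Baseline is the latest available value before the first ticagrelor dose (Day -2 pre-dose, otherwise Day -3), and %baseline = 100 × post-dose value / PD Baseline. Limit the Section 4 rule to non-PD data. Report Hour 0 separately as the on-ticagrelor, pre-infusion value. Preferring Day -2 to Day -3 is a reasonable choice rather than a protocol requirement; either draw satisfies the protocol, but one must be named.

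The cost is two SAP sentences and a check of the PD derivation. The Day -3 and Day -2 draws are already in the schedule, so no new samples are needed. The documents do not say whether the database is locked. If PD outputs already exist, check which denominator was used and record it in SAP Section 13.

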4.1. Sample Size

The sample size (N) of up to 5 cohorts (Part A) up to 3 cohorts (Part B) of up to 12 subjects per cohort for this study is based on clinical and practical considerations rather than on formal statistical power calculation. The sample size is considered sufficient to adequately assess the safety, PK, and PD profiles of PB2452 and the PK and PD profiles of ticagrelor and its active metabolite TAM.

4.2. Randomization, Stratification, and Blinding

This is a double-blind study. Neither the subjects nor the investigator will be aware of the treatment assignment. Blinding will be maintained throughout the study by use of active and placebo dose forms prepared to be similar in appearance. Subjects will be randomized in a 3:1 (PB2452:placebo) ratio. No stratification will be utilized.

In order to prepare preliminary summaries of safety, PK, and/or PD data, as needed, to make timely decisions concerning adjustment of study procedures, dosing regimens, or potentially

early termination of the study, certain designated staff at PhaseBio (e.g., study director, a single biostatistician, and bioanalytical scientist[s], study drug accountability monitor) will receive unblinded data after each cohort completes Day 3 assessments.

The scheduled unblinding event to all study members will occur after the database is locked (hard-locked).

4.3. Replacements

At the discretion of the investigator after consultation with the Sponsor, any subject who withdraws before completing the study, for reasons other than a dose-limiting toxicity (DLT), may be replaced. Any replacement subject will be assigned to receive the same treatment as the subject he or she is replacing.

4.4. Handling of Missing data

For the purpose of determining inclusion of AEs in the treatment-emergent AE (TEAE) summary tables, incomplete or missing AE onset and end dates will be imputed as follows:

Incomplete or missing onset dates (where UK and UNK indicate unknown or missing day and month, respectively):

- UK-MMM-YYYY: If the month and year are different from the month and year of the dose of study drug, assume 01-MMM-YYYY. If the month and year are the same as the dose of study drug month and year, and the end date (after any imputation) is on or after the dose of study drug, then assume the date of the dose of study drug. If the month and year are the same as the dose of study drug month and year and the end date (after any imputation) is prior to the dose of study drug, then assume the end date for the onset date.
- DD-UNK-YYYY or UK-UNK-YYYY: If the year is different from the year of dose of study drug, assume DD-JAN-YYYY or 01-JAN-YYYY of the onset year, respectively. If the year is the same as the dose of study drug year, and the end date (after any imputation) is on or after the dose of study drug, then assume the date of the dose of study drug. If the year is the same as the dose of study drug, and the end date (after any imputation) is prior to the dose of study drug, then assume the end date for the onset date.
- Missing onset date: If the onset date is completely missing and the end date (after any imputation) is on or after the dose of study drug, then assume the date of the first dose of study drug. If the end date (after any imputation) is prior to the dose of study drug, then assume the end date for the onset date.

Incomplete or missing end dates (where UK and UNK indicate unknown or missing day and month respectively):

- UK-MMM-YYYY: Assume the last day of the month;
- DD-UNK-YYYY or UK-UNK-YYYY: Assume DD-DEC-YYYY or 31-DEC-YYYY, respectively;

- Missing end date: Assume 31-DEC-YYYY, where YYYY is the year of the dose of study drug.

An AE with missing onset time but with an onset date the same as the dosing date of study drug will be classified as treatment-emergent, unless the AE was reported pre-dose with the same or worse intensity or frequency.

Medications with missing start time but with a start date the same as the dosing date of study drug will be considered as being taken on or after the initiation of study drug, unless the electronic case report form (eCRF) question “Was the medication/therapy taken prior to the study” is answered as “Yes” which is considered as being taken prior to the initiation of study drug.

Handling of missing PK data is specified in Section 10 and handling of PD data is specified in Section 11.

